	APPENDIX 1-2: DATA COLLECTED FROM PHARMACY CARD	45
	APPENDIX 2-1: PRO INSTRUMENTS – WORK PRODUCTIVITY AND ACTIVITY IMPAIRMENT QUESTIONNAIRE SPECIFIC HEALTH PROBLEM V2.0 (WPAI:SHP)	46

APPENDIX 2-2: PRO INSTRUMENTS – WORK LIMITATIONS QUESTIONNAIRE 8-ITEM SELF-ADMINISTERED SHORT FORM (WLQ-8)..... 48

APPENDIX 3: CAUSALITY AND OUTCOME DEFINITIONS FOR SERIOUS ADVERSE EVENT (SAE) REPORTING 56

SYNOPSIS

Title: Real world effectiveness of combining an employer-based weight management program with medication for chronic weight management in employees with obesity – a pragmatic randomized trial

Sponsor: Novo Nordisk
 
Study Treatment: Cleveland Clinic’s Integrated Medical Weight Management Program (WMP) with medication approved for chronic weight management in the US, i.e., “WMP + Rx”
 
Active Ingredient: One of following approved medications: orlistat (per os (p.o.)), lorcaserin or lorcaserin extended-release (p.o.), phentermine/topiramate extended-release (p.o.), naltrexone/bupropion extended-release (p.o.), liraglutide 3.0 mg (subcutaneous (s.c.))
 
Comparator Treatment: Cleveland Clinic’s Integrated Medical WMP with no medication for weight management, i.e., “WMP”

Protocol No.: NN8022-4432

Study Site: This is a single-center study conducted at the Cleveland Clinic’s Endocrinology and Metabolism Institute, Cleveland, Ohio.
 
Country: United States

Subjects: Eligible subjects include adults with obesity (body mass index (BMI) ≥ 30 kg/m²) enrolled in the Cleveland Clinic Employee Health Plan for whom treatment with medication for chronic weight management may be indicated.
 
Planned enrollment in this study is 200. Subjects will be randomized 1:1 to receive either WMP + Rx or WMP alone.


Study Objectives: The objectives of this study are as follows:
 
 • The primary objective is to demonstrate superior effect of treatment with an employer-based weight management program in combination with medication for chronic weight management compared to an employer-based weight management program alone in subjects with obesity on weight loss. • The secondary objectives are to compare the effects of treatment with an employer-based weight management program in combination with medication for chronic weight management to an employer-based weight management program alone in subjects with obesity with regards to: 
 ○ Categorical weight loss ○ Adherence to the weight management program ○ Patient-reported outcomes (PROs) on work productivity and work limitations • Furthermore, the secondary objectives will assess adherence to medication for chronic weight management (only in the treatment arm randomized to an employer-based chronic weight management program with medication for chronic weight management).

Study Design: This is a one-year, single-center, randomized, open-label, parallel-group pragmatic clinical trial (PCT) comparing Cleveland Clinic’s existing Integrated Medical WMP combined with

medication for chronic weight management versus Cleveland Clinic's existing Integrated Medical WMP with no medication for weight management in subjects with obesity. Subjects will be randomized 1:1 to receive either Cleveland Clinic's Integrated Medical WMP with medication for chronic weight management ("WMP + Rx") or Cleveland Clinic's Integrated Medical WMP alone ("WMP").

To preserve the real-world nature of the study, the subject experience will be as close to routine clinical care as possible. The weight management program provided to all study subjects will be similar to the Integrated Medical WMP that is currently offered by the Cleveland Clinic. Consistent with standard practice of the Integrated Medical WMP, subjects in both treatment groups will attend monthly shared medical appointments (SMAs) and will be responsible for a co-payment. In the WMP + Rx arm, obesity medications approved by the Food and Drug Administration (FDA) for chronic weight management are allowed and selection of specific medication is at the discretion of the study clinician. To simulate the co-payment that would be applied if a health plan covered treatment with medications for chronic weight management, subjects will pay a set fee for the obesity medication.

Study visits include an individual screening and randomization visit (visit 1; informed consent must be obtained at visit 1 before screening), followed by twelve once-monthly visits set up in the context of SMAs (visit 2 to visit 13). All subjects will be referred to a nutritionist appointment between visit 1 and visit 2. End of Study (EOS) is visit 13 (month 12 (-14 days, +28 days)). Effort will be made to obtain a month 12 (visit 13) weight measurement from all randomized subjects, unless they have withdrawn consent. There will not be a follow-up period.

Subject Selection:Inclusion Criteria:

Subjects must meet all of the following inclusion criteria to be eligible for the study:

1. Informed consent obtained before any study-related activities. Study-related activities are any procedures that are carried out as part of the study, including activities to determine eligibility for the study.
2. Male or female, age ≥ 18 years at the time of signing informed consent
3. Body mass index (BMI) ≥ 30 kg/m²
4. Enrolled in Cleveland Clinic Employee Health Plan, and expecting to be covered by the Cleveland Clinic Employee Health Plan for the duration of the study

Exclusion Criteria:

Subjects presenting with any of the following exclusion criteria will not be eligible for the study:

1. Contraindications to all of the medications approved by the FDA for chronic weight management according to the label.
2. Previous participation in this study. Participation is defined as signed informed consent.
3. Female who is pregnant, breast-feeding or intends to become pregnant or is of child-bearing potential and not using adequate contraceptive methods (adequate contraceptive measures as required by local regulation or practice).
4. Participation in another clinical trial within 30 days before screening.
5. Treatment with any medication with the intention of weight loss within 90 days before screening.

6. Previous or current participation in Cleveland Clinic's Integrated Medical Weight Management Program.
7. History of (or plans during the study period for) bariatric surgery, or use of minimally-invasive weight loss devices (i.e., intragastric balloons, lap bands) not removed within 1 year prior to screening.
8. History of type 1 or type 2 diabetes mellitus.
9. HbA1c \geq 6.5% at screening or within 90 days prior to randomization.
10. Any condition, unwillingness or inability, not covered by any of the other exclusion criteria, which, in the study clinician's opinion, might jeopardize the subject's safety or compliance with the protocol.

Study Procedures:

- Potentially eligible subjects will be identified during the course of routine implementation of Cleveland Clinic's Employee Wellness Program, "Healthy Choice," or referred to the study via the study advertisement or another health care provider.
- Study clinicians will obtain informed written consent from subjects and if eligible, subjects will be randomized to either WMP + Rx or WMP.
- Study data will be collected on electronic Case Report Forms (eCRFs) via an electronic data capture (EDC) system.
- Assessments at the screening and randomization visit (visit 1/baseline (month 0)) include: eligibility (including urine pregnancy test (if applicable) and point of care (POC) hemoglobin A1c (HbA1c) measurement if an HbA1c measurement is not available within 90 days prior to randomization), demographic data, relevant medical history, concomitant medications, height, and body weight.
- All subjects will enroll in the Integrated Medical WMP at the Cleveland Clinic's Endocrinology and Metabolism Institute. In this program, as part of usual care, subjects will:
 - discuss and choose one of three diet options: protein-sparing modified fast, Mediterranean, or meal replacement.
 - be referred to a nutritionist appointment.
 - initiate a series of twelve monthly study visits (visits 2-13) in the context of SMAs covering nutrition, physical activity, appetite control, sleep issues, and anxiety/depression/stress.
 - be referred to an exercise physiologist for a personalized physical activity program.
 - if assessed relevant by the study clinician, be referred to a mental health specialist and/or sleep clinic.
- Subjects enrolled in the WMP + Rx arm will be provided a prescription for medication indicated for chronic weight management (obesity medication) at the time of randomization (visit 1).
- Disallowed medications:

- Other than the medication prescribed by the study clinician for chronic weight management in the WMP + Rx arm, use of any medication, on- or off-label, for weight loss purposes is not allowed in either arm during the study.
- The use of glucagon-like peptide-1 receptor agonists (GLP-1 RAs) and sodium-glucose co-transporter 2 (SGLT-2) inhibitors for diabetes diagnosed during the study is not allowed.
- Assessments during monthly study (i.e., SMA) visits include: weight, pregnancy and serious adverse events (SAEs), attendance at SMAs, and use of disallowed medications.
- Prescription fill data for obesity medication (WMP + Rx arm) will be collected from randomization through EOS.
- **Questionnaires:** PROs on work productivity and work limitations will be assessed by the Work Productivity and Activity Impairment Questionnaire Specific Health Problem v2.0 (WPAI:SHP) and the Work Limitations Questionnaire 8-Item (WLQ-8) Self-administered Short Form at visit 1, visit 7, and visit 13.

Study Duration: Total study duration for the individual subjects will be approximately one year. Subjects will be followed and data collection will continue for the full duration of the study, unless the subject withdraws informed consent. The full duration of the study is defined as up to and including visit 13. Effort will be made to obtain a month 12 (visit 13) weight measurement from all randomized subjects.

Analysis: Two estimands, each targeting a unique research question, have been defined to adequately describe the effect of an employer-based WMP combined with obesity medication compared to an employer-based WMP alone.

The primary estimand for all endpoints is an “intention-to-treat” estimand. This estimand will quantify the average treatment effect of an employer-based WMP combined with medication for chronic weight management compared to the employer-based WMP alone after 12 months, in all randomized subjects and regardless of adherence to randomized treatment.

The secondary estimand for body weight loss, categorical weight loss, and PROs is an “if all subjects had adhered” estimand. This estimand will quantify the average treatment effect of an employer-based WMP combined with medication for chronic weight management compared to the employer-based WMP alone after 12 months, in all randomized subjects had they adhered to their randomized treatment for the entire planned study duration.

The primary endpoint is percent change in body weight from baseline (month 0) to month 12 (visit 13). The study is designed to have 80% power to confirm superiority of WMP + Rx versus WMP alone on % weight change from baseline (month 0) to month 12 (visit 13).

The full analysis set (FAS) comprising all randomized subjects analyzed according to the treatment group to which they were assigned at randomization will be the analysis population for the evaluation of both the primary and secondary estimands. The primary estimand will be estimated based on the FAS and % weight change will be modeled using linear regression (Analysis of Covariance (ANCOVA)) with randomized treatment as a factor and baseline body weight (kg) as a covariate. Prior to analysis, missing month 12 weight data will be imputed by multiple imputations. For the secondary estimand, the primary endpoint will be analyzed using a mixed model for repeated measurements (MMRM) including all subjects, but for subjects considered non-adherent to randomized treatment, only data prior to non-adherence will be used.

The significance level used in all statistical analyses will be 5% (two-sided).

Supplementary Analyses: A supplementary analysis will be conducted on the subset of subjects with month 12 (visit 13) body weight data who adhered to randomized treatment up to and including visit 13.

Secondary Analyses: Secondary analyses will compare WMP + Rx versus WMP in terms of categorical weight loss, adherence to the WMP, and PRO measures. Additionally, adherence to obesity medication will be descriptively summarized for the WMP + Rx arm. The primary estimand will be assessed for all secondary endpoints. Additionally, the secondary estimand will be assessed for categorical weight loss and PRO measures.

Safety: For the purposes of this study, adverse events (AEs) will only be required to be collected if they meet the definition of an SAE. Study clinicians are responsible for reporting all SAEs and following the subject until the outcome of the event is closed out. All SAEs will be reported from randomization until EOS at month 12, or until the subject withdraws from the study. Study clinicians are also responsible for recording all pregnancies in female subjects from randomization until EOS at month 12 or subject study withdrawal. The subject will be followed for the duration of the pregnancy until one month post-delivery to report the pregnancy outcome and any AEs or SAEs observed in the fetus or newborn until 1 month of age. Safety will be summarized descriptively.

LIST OF ABBREVIATIONS

Abbreviation	Definition
AE	Adverse Event
ANCOVA	Analysis of Covariance
API	Active Pharmaceutical Ingredient
BMI	Body Mass Index
eCCG	Electronic Case Report Form Completion Guidelines
CFR	Code of Federal Regulations
CI	Confidence Interval
eCRF	Electronic Case Report Form
EDC	Electronic Data Capture
EMR	Electronic Medical Record
EOS	End of Study
FAS	Full Analysis Set
FDA	Food and Drug Administration
FDAAA	Food and Drug Administration Amendment Act
GCP	Good Clinical Practice
GLP-1 RA	Glucagon-Like Peptide-1 Receptor Agonists
HbA1c	Hemoglobin A1c
HIPAA	Health Insurance Portability and Accountability Act
ICF	Informed Consent Form
ICMJE	International Committee of Medical Journal Editors

Abbreviation	Definition
IRB	Institutional Review Board
LSFV	Last Subject First Visit
MedDRA	Medical Dictionary for Regulatory Activities
MMRM	Mixed Model for Repeated Measurements
OR	Odds Ratio
PCD	Primary Completion Date
PCT	Pragmatic Clinical Trial
PDC	Proportion of Days Covered
PO	Per Os
POC	Point of Care
PRO	Patient Reported Outcome
PT	Preferred Term
SAE	Serious Adverse Event
SAP	Statistical Analysis Plan
SC	Subcutaneous
SD	Standard Deviation
SGLT-2	Sodium-Glucose Co-transporter 2
SMA	Shared Medical Appointment
SOC	System Organ Class
US	United States
WLQ-8	Work Limitations Questionnaire 8-Item

Abbreviation	Definition
WMP	Weight Management Program
WPAI:SHP	Work Productivity and Activity Impairment Questionnaire Specific Health Problem

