5.2.2.3 Concomitant medications

Concomitant medications for medical conditions other than obesity are allowed in both treatment arms at the discretion of the study clinician, except for the use of glucagon-like peptide-1 receptor agonists (GLP-1 RAs) and sodium-glucose co-transporter 2 (SGLT-2) inhibitors for diabetes diagnosed during the study. Other than the medication prescribed by the study clinician for chronic weight management in the WMP + Rx arm (section 5.2.2.2), use of any medication, on- or off-label, for weight loss purposes is not allowed in either arm during the study. Through routine medication review during SMA study visits, use of medications that are not allowed per protocol (i.e., “disallowed”) will be identified and will be indicated in the eCRF. The subject will remain in the study.

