6.4.3 Secondary Estimand for the Primary Endpoint

The secondary estimand of the primary endpoint will address the efficacy of medication for chronic weight management if all subjects adhere to their randomized treatment (WMP + Rx or WMP). For the secondary estimand, the primary endpoint will be analyzed using a mixed model for repeated measurements (MMRM) including all subjects, but for subjects considered non-adherent to randomized treatment, only data prior to non-adherence will be used. Month 12 (visit 13) assessments for retrieved drop outs will not be used in this analysis. The MMRM for efficacy will only use assessments from subjects who are adherent to the randomized treatment until end of treatment, or up until the subject is considered non-adherent to the randomized treatment. Subjects in the WMP arm will be considered non-adherent if/when criterion 1 below is met. Subjects in the WMP + Rx arm will be considered non-adherent if/when criterion 1 or 2 is met:

1. Missing 4 SMA visits. In this case, the last assessment made prior to the 4th missed SMA visit will be used as the last assessment. This is also the case if, e.g., 4 SMA visits in a row are missed.
2. Period with no coverage of prescription claims according to PDC exceeds 20% of planned medication duration, or number of days from visit 1 to visit 13. For subjects that drop out early, the expected visit 13 date (derived from the subjects' planned SMA group visit) will be used to calculate planned study duration. The last assessment made prior to exceeding 20% of planned study duration with no prescription claims will be used as last assessment.

The MMRM for efficacy will be fitted using % weight change with randomized treatment as factor and baseline body weight (kg) as covariate, all nested within visit. An unstructured covariance matrix for measurements within the same subject will be employed, assuming that measurements for different subjects are independent.

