5.6.2 Statistical Analysis for the Secondary Estimand

The secondary estimand of the primary endpoint will address the efficacy of medication for chronic weight management if all subjects adhere to their randomized treatment (WMP + Rx or WMP). For the secondary estimand, the primary endpoint will be analyzed using a mixed model for repeated measurements (MMRM) including all subjects, but for subjects considered non-adherent to randomized treatment, only data prior to non-adherence will be used. Month 12 (visit 13) assessments for retrieved drop outs will not be used in this analysis. The MMRM for efficacy will only use assessments from subjects who are adherent to the randomized treatment until end of treatment, or up until the subject is considered non-adherent to the randomized treatment. Subjects in the WMP arm will be considered non-adherent if/when criterion 1 below is met. Subjects in the WMP + Rx arm will be considered non-adherent if/when criterion 1 or 2 is met:

1. Missing 4 SMA visits. In this case, the last assessment made prior to the 4th missed SMA visit will be used as the last assessment. This is also the case if, e.g., 4 SMA visits in a row are missed.
2. Period with no coverage of prescription claims according to PDC exceeds 20% of planned medication duration, or number of days from visit 1 to visit 13. For subjects that drop out early, the expected visit 13 date (derived from the subjects' planned SMA group visit) will be used to calculate planned study duration. The last assessment made prior to exceeding 20% of planned study duration with no prescription claims will be used as last assessment (as defined in Section 4.8.5).

The MMRM for efficacy will be fitted using % weight change with randomized treatment as factor and baseline body weight (kg) as covariate, all nested within visit. An unstructured covariance matrix for measurements within the same subject will be employed, assuming that measurements for different subjects are independent. From the model, treatment effect will be estimated and reported along with the associated 95% CI and corresponding p-value testing the null-hypothesis of no difference between treatment arms.

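### Bariatric surgery, a weight-loss device or a disallowed weight-loss drug after randomization does not end data use in the if-all-adhered analyses (minor)

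*Protocol*

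**What the plan says.** **Entry.** Exclusion criterion 7 (Protocol Synopsis and 4.2.4) bars "History of (or plans during the study period for) bariatric surgery, or use of minimally-invasive weight loss devices", with a condition on when a device was removed. It acts at screening only.

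**Follow-up data.** The Protocol Synopsis lists the monthly items: "Assessments during monthly study (i.e., SMA) visits include: weight, pregnancy and serious adverse events (SAEs), attendance at SMAs, and use of disallowed medications". Protocol 5.4 and Appendix 1-1 agree, and medical history is a visit 1 item. No item asks about a procedure.

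**Disallowed treatment.** Protocol 5.2.2.3 states that, apart from the medication prescribed in WMP + Rx, "use of any medication, on- or off-label, for weight loss purposes is not allowed in either arm during the study". Such use is looked for "Through routine medication review during SMA study visits" and marked in the eCRF, and the subject stays in the study. SAP 5.9 tabulates it. Both sections concern medications only.

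**Secondary estimand.** In the MMRM, "for subjects considered non-adherent to randomized treatment, only data prior to non-adherence will be used". Protocol 6.4.3 gives two triggers. The first is "Missing 4 SMA visits. In this case, the last assessment made prior to the 4th missed SMA visit will be used" as the last one. The second is "Period with no coverage of prescription claims according to PDC exceeds 20% of planned medication duration". The SAP repeats both and limits the control arm to the first: "Subjects in the WMP arm will be considered non-adherent if/when criterion 1 below is met". WMP + Rx is subject to either.

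**Reach.** The same classification governs the completer analysis (Protocol 6.4.4, SAP 5.6.3), the secondary-estimand responder analyses (SAP 5.7.2.1) and the PRO MMRM (SAP 5.7.2.2).

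**The concern.** The secondary estimand is meant to show what medication adds if everyone follows the randomized treatment. A procedure is part of neither arm's treatment, and the comparator is defined as the program without weight-management medication. Yet a WMP subject who has surgery, receives a device or takes a weight-loss drug, and misses fewer than four SMAs, is classed as adherent through visit 13. Every later weight counts as an effect of WMP. The same happens in WMP + Rx as long as fills continue.

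At stake is the meaning of the efficacy estimate and of the completer, responder and PRO results that borrow its rule. Without a date field for procedures, the sponsor also cannot reliably find such cases or show that there were none. Their handling could then be decided only after the data are seen.

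**Working it through.** **1. Events against the rule**

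| Event after randomization | Planned record | Ends data use in WMP? | Ends data use in WMP + Rx? |
|---|---|---|---|
| Bariatric surgery or device | No dedicated field; may surface as an SAE (Protocol 7.2) or a major deviation (SAP 5.4) | Only through a fourth missed SMA | Fourth missed SMA, or gap above 20% |
| Disallowed weight-loss drug | eCRF item at visits 2-13 | Only through a fourth missed SMA | Fourth missed SMA, or gap above 20% |

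Neither event is itself a trigger in either arm. The arms differ only in the fill-gap route.

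**2. How far the fill-gap route reaches.** Taking 365 days as the planned duration, 20% is 0.20 × 365 = 73 days without cover, counted cumulatively. A WMP + Rx subject who stops filling after a procedure contributes weights until that total is passed. With no earlier gaps, a stop after about day 365 − 73 = 292 never triggers the rule. A subject who keeps filling is never cut. The asymmetry is therefore partial.

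**3. The plan's own figure.** Protocol Table 6-1 gives power 0.80 for 200 subjects, a 4-point effect and SD 10. A two-sided t-test at 5% with 100 per arm gives 0.804, so the figure reproduces and is not in dispute. The SD and the 4-point effect serve below as the yardstick.

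**4. Size of one case.** The documents give neither the number of such events nor their effect on weight. Assumptions:
- extra loss e = 10 to 25 points per case;
- contributing subjects in the arm n = 50 to 100. The lower end takes the 50% drop-out of Protocol 6.3.1 as a stand-in for non-adherence, which is defined differently; the upper end is the whole arm.

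Shift in the arm mean for k cases = k × e / n. This is a simple-mean approximation to the MMRM.

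| k = 1 | e = 10 | e = 20 | e = 25 |
|---|---|---|---|
| n = 50 | 0.20 | 0.40 | 0.50 |
| n = 100 | 0.10 | 0.20 | 0.25 |

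Against the 4-point planning effect, the range is 0.10/4 = 2.5% to 0.50/4 = 12.5%.

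**5. Against sampling error.** With SD 10, the standard error of the difference is √(100/50 + 100/50) = 2.0 points at 50 per arm and √(100/100 + 100/100) = 1.41 at 100 per arm. One case is therefore 0.20/2.0 = 0.10 to 0.50/2.0 = 0.25 standard errors at n = 50, and 0.10/1.41 = 0.07 to 0.25/1.41 = 0.18 at n = 100.

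**6. Several cases.** The shift is linear in k. At n = 50 and e = 20, two cases in one arm give 0.8 points and five give 2.0. The documents offer no ground for expecting any particular number.

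**7. Direction.** Extra loss in WMP shrinks the estimated benefit of medication. Extra loss in WMP + Rx with continued fills enlarges it.

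**The case against.** The strongest reply is that the plan is consistent on its own terms. Protocol 6.1.1 and SAP 4.2.2 define adherence by reference to the two criteria, so a WMP subject who attends has adhered by definition. That stands to this extent: the text does not contradict itself, and criterion 7 is sound as an entry rule. But Protocol 6.4.3 states that the aim is the efficacy of medication if all adhere to their randomized arm. Counting a subject on a disallowed weight-loss drug as adherent to an arm defined by having none does not serve that aim.

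Three stronger readings are tempting, and the documents do not support them.

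- *The plan cannot see procedures at all.* An inpatient stay may be reported as an SAE, SAP 5.4 summarizes major deviations, and Protocol section 5 allows extraction from medical records. Capture is not assured, however: elective surgery is not clearly an adverse event, and none of these records feeds the adherence rule.
- *The censoring reliably pushes the difference toward zero.* That would require cases to fall in WMP, or WMP + Rx cases to stop filling early enough to be cut. Neither is given.
- *One case is an extreme outlier that could decide the result.* At SD 10, an extra 10-25 points is 1.0 to 2.5 SD, and the shift in the mean is at most about a quarter of a standard error.

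Events are also likely to be few, since surgery planned for the study year is excluded, and SAP 3.2 makes all secondary endpoints supportive. These points limit the severity but do not close the gap.

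**Conclusion.** The gap is real and minor. Surgery, a device or a disallowed weight-loss drug does not end data use in either arm, so its effect on weight or PROs can be credited to the randomized treatment in the secondary-estimand analyses and the completer analysis. The sign depends on the arm in which cases fall, with a partial asymmetry because only WMP + Rx has the fill-gap trigger.

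The size, about 0.1-0.5 points per case, rests wholly on the assumed extra loss and number of contributing subjects. It is small beside the sampling error.

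A reader might infer that the superiority claim is at risk. The documents do not support that: the single confirmatory test uses the treatment-policy estimand, which properly keeps these weights. Post-procedure visit 13 weights in WMP would also inform the imputation for both arms under SAP 5.5.1, but no change to the primary analysis is asked for here.

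**What to change.** In Protocol 6.4.3 and SAP 5.6.2, add a third criterion for both arms, along these lines: *Bariatric surgery, placement of a weight-loss device, or start of a disallowed weight-loss medication; the last assessment before that date is the last assessment used.* State that it applies to the completer analysis and to the secondary-estimand responder and PRO analyses. Say whether the GLP-1 RAs and SGLT-2 inhibitors for diabetes that SAP 5.9 also lists as disallowed count under it.

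Record procedure (yes/no, date) at the existing SMA review. For visits already past, extract it from medical records before database lock; this matters because SAP version 2 was written after first patient first visit. Tabulate it by arm alongside SAP 5.9. Disallowed medication is already marked visit by visit, which dates it to about a month. Leave the primary estimand as it is.

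The cost is some wording, one eCRF item and a records check, and a few late weights leave non-confirmatory analyses. The change concerns recording and data use only and alters no clinical rule.
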